10.4.4.2. DCR

Disease control rate (DCR) will be analyzed using the same methodology as that for ORR.

10.4.4.3. Time to Deterioration of ECOG Performance Status

Time to deterioration of ECOG performance status to a score of 2 or higher will be analyzed using methodology described in [Section 10.4.1](#). Patients not reaching an ECOG of 2 or more (3, 4 or 5) will be censored at the last recorded ECOG assessment. CCI

Assignment of the ECOG Performance Status results to the appropriate cycle will be executed according to the instructions displayed in CCI. Additionally, if multiple ECOG status outcomes are reported at an analysis time window (refer to [Section 8.7](#) CCI), then the logic described in [Section 8.8](#) and specific data handling rules presented in CCI will be applied.

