10.2.8. Survival Follow-up after 30-Day Safety Visit

The following assessments should be obtained at scheduled 4-week (± 7 days) time intervals during the survival follow-up period:

- Tumor measurement (by CT scan, see Section 11) every 8 weeks until radiologic disease progression (for patients who discontinued treatment for reasons other than disease progression) or initiation of new anticancer therapy (whichever occurs first)
- Concomitant medications collect antitumor therapies only
- Contact patient/caregiver to determine survival status (alive/dead)
- SAE collection only if the SAE is related to study medication

Patients will be followed for survival until the target number of events is reached. The Investigators will be informed when this target is reached.

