Key Secondary Efficacy Endpoint (PFS)

PFS will be evaluated from date of randomization to the first occurrence of radiologic progression or death. Treatment comparisons for PFS will use similar analytical methods as the OS endpoint.

Other Secondary Efficacy Endpoints

ORR and DCR will be compared between treatment arms using Fisher's exact test and associated 95% CIs will also be derived. Time to deterioration of ECOG performance status to a score of 2 or higher will be analyzed as described for PFS. Change in QoL scores prior to cycles 2, 3 and 4 will be determined for the summary, all domains and single items by subtracting each patient's score from their corresponding baseline score. For each domain, the proportion of patients with deteriorating (vs stable or improving) scores prior to cycles 2, 3 and 4 will be compared using Fisher's exact test. Time to QoL deterioration will be evaluated for each arm using Kaplan-Meier estimates and compared using the log-rank test.

Safety Analyses

Simple descriptive statistics will be provided for safety endpoints and demographic/baseline characteristics.

TABLE OF CONTENTS

1.	LIST OF ABBREVIATIONS.....	11
2.	INTRODUCTION.....	15
3.	STUDY OBJECTIVES AND ENDPOINTS.....	16
3.1.	Study Objectives.....	16
3.1.1.	Primary Objective.....	16
3.1.2.	Key Secondary Objectives.....	16
3.1.3.	Other Secondary Objectives.....	16
3.2.	Study Endpoints.....	16
3.2.1.	Primary Efficacy Endpoint.....	16
3.2.2.	Key Secondary Efficacy Endpoints.....	17
3.2.3.	Other Secondary Efficacy Endpoints.....	17
4.	STUDY DESIGN.....	19
4.1.	Summary of Study Design.....	19
4.2.	Definition of Study Drugs.....	20
4.3.	Sample Size Considerations.....	21
4.3.1.	Sample Size Justifications.....	21
4.4.	Randomization.....	21
4.5.	Clinical Assessments.....	21
4.5.1.	Vital Signs, Height and Weight.....	21
4.5.2.	Performance Status.....	21
4.5.3.	Laboratory Evaluations.....	22
4.5.4.	Pregnancy Testing.....	22
4.5.5.	Quality of Life.....	23
4.5.6.	Tumor Measurements.....	23
4.5.7.	Concomitant Medications.....	24
5.	PLANNED ANALYSES.....	25
5.1.	Interim Analyses.....	25
5.2.	Final Analyses.....	25
6.	STUDY DURATION AND VISIT SCHEDULE.....	26
7.	ANALYSIS POPULATIONS.....	29
7.1.	Intent-To-Treat (ITT) Population.....	29

7.2.	As-Treated (AT) Population (Safety Population).....	29
7.3.	Tumor Response(TR) Population.....	29
8.	DERIVED AND TRANSFORMED DATA	30
8.1.	Age (relatively to Informed Consent Date).....	30
8.2.	Study Day	30
8.3.	Baseline.....	30

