3.2.2. Key Secondary Efficacy Endpoints

Progression free survival (PFS) will serve as a key secondary efficacy endpoint of the study. PFS is defined as the time from the date of randomization until the date of the investigator-assessed radiological disease progression or death due to any cause. Patients who are alive with no disease progression as of the analysis cut-off date will be censored at the date of the last tumor assessment. Patients who receive non-study cancer treatment before disease progression, or patients with clinical but not radiologic evidence of progression will be censored at the date of the last radiologic evaluable tumor assessment before the non-study cancer treatment is initiated **CC**

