3.2.3.3. Time to Deterioration of ECOG Performance Status

The time to deterioration of ECOG performance status is defined as the time from randomization to the first date on which an ECOG performance status score of 2 or higher is observed. Patients not reaching an ECOG of 2 or more will be censored at the last recorded ECOG assessment on study.

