4.3. Sample Size Considerations

4.3.1. Sample Size Justifications

The study is designed to detect with 90% power a hazard ratio for death of 0.70 (30% risk reduction) in the TAS-102 arm compared with the placebo arm with an overall 1-sided type 1 error of 0.025. A variable accrual period of 18 months and a 5%/year loss to survival follow-up rate has been assumed. Using a treatment allocation of 2:1 (TAS-102:placebo) of 500 patients, 384 deaths will be targeted for the final OS analysis.

Based on these design operating characteristics and assuming a median survival time of approximately 5 months in the control arm, the primary analysis target events milestone will be reached approximately 8 months after the last patient is randomized in the study. The median OS in the control arm was estimated based on the observed median OS of 3.8 months in the placebo arm of the 2nd line Phase 3 ramucirumab (REGARD) study, and the observed median OS of 4.3 months in the placebo arm of the 2nd & 3rd line Phase 3 everolimus (GRANITE) study [13]. The estimate was further increased to 5 months to account for the higher control median projected in the Japanese population.

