4.5.2. Performance Status

Patient's performance status (ECOG) will be collected at the following time points (Table 2).

- Within 28 days prior to Day 1 of Cycle 1
- At time of randomization (within 3 calendar days prior to start of study treatment on Day 1 of Cycle 1)

- Beginning with Cycle 2, obtain within 24 hours prior to start of study treatment in every cycle
- End of Treatment Visit (if applicable)
- 30-day Safety Follow-up Visit

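### Time to ECOG 2 or higher has no consistent visible rule for death: score 5 is listed as reaching the event, yet patients with no recorded score of 2 or more are censored at the last ECOG visit

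*SAP*

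**What the plan says.** **Definition.** SAP 3.2.3.3 counts from randomization to "the first date on which an ECOG performance status score of 2 or higher is observed", and adds: "Patients not reaching an ECOG of 2 or more will be censored at the last recorded ECOG assessment on study". Protocol 13.2.3.3 gives the same definition without a censoring sentence.

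**Analysis.** SAP 10.4.4.3 states: "Patients not reaching an ECOG of 2 or more (3, 4 or 5) will be censored at the last recorded ECOG assessment". Protocol 13.3.2.3 has the same sentence. Both sections refer to the primary OS methodology. In the SAP, blacked-out text follows directly; in the Protocol, the Quality of Life paragraph follows.

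**Synopses.** The Protocol and SAP synopses both say: "Time to deterioration of ECOG performance status to a score of 2 or higher will be analyzed as described for PFS". The PFS event in SAP 3.2.2 is "investigator-assessed radiological disease progression or death due to any cause".

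**Collection.** SAP 4.5.2 and Protocol 10.1.9 schedule ECOG within 28 days before Cycle 1, at randomization, then "Beginning with Cycle 2, obtain within 24 hours prior to start of study treatment in every cycle", at the End of Treatment visit if there is one, and at the 30-day safety visit. Survival follow-up (Protocol 10.2.8) collects vital status but not ECOG.

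**Missing data and testing.** SAP 8.13.1 does not impute missing efficacy data unless a rule says so. SAP 10.4.4 tests this endpoint at the 2-sided 0.05 level.

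**The concern.** The visible documents do not define ECOG score 5. I take it to be death, the usual convention for the scale. On that footing the analysis sections treat a death as having reached the endpoint, while the definition sections require a score observed at an assessment. No visible text says that a death is entered as score 5, or that the date of death is the event date.

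Two programmers working from this text could therefore produce different analyses. If deaths are not scored, every patient who dies without an earlier recorded 2 or higher leaves the risk set at the last ECOG visit. Log-rank and Cox methods need censoring to be unrelated to the event, and decline in performance status and death are plainly related.

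The endpoint can carry a clinical message. Protocol 6.2.3 cites a 34% risk reduction on the same measure in the earlier colorectal trial as a sign that quality of life was maintained. A similar statement from this trial would depend on which death rule was used.

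**Working it through.** **1. The passages side by side**

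| Place | Points toward |
|---|---|
| SAP 10.4.4.3 and Protocol 13.3.2.3 (score 5 in the bracket) | Death is an event, if deaths are entered as 5 |
| Both synopses (as for PFS) | Death is an event |
| SAP 3.2.3.3 and Protocol 13.2.3.3 (score must be observed) | Death is not an event unless scored |
| SAP 8.13.1 (no imputation without a rule) | A missing score 5 is not created from a death date |
| ECOG schedule (ends at the 30-day visit) | Later deaths have no ECOG record |

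Coverage can be thinner than scheduled. The End of Treatment visit is not required when the decision to stop falls within 2 weeks of the last treatment visit (Protocol 10.2.6), and a telephone call may replace the 30-day visit when new therapy starts (Protocol 10.2.7). Living patients off treatment are also censored at their last ECOG visit. By contrast, death handling is explicit for PFS (an event) and for time to QoL deterioration (death date listed as a censoring point, SAP 10.4.4.4.6).

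**2. The plan's own figure**

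No event count or power is given for this endpoint. The only design figure is for OS: 384 deaths, HR 0.70, 90% power, 1-sided 0.025, 2:1 allocation.

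- Events needed (Schoenfeld) = (1.960 + 1.282)² / [(2/3)(1/3)(ln 0.70)²] = 10.51 / (0.2222 × 0.1272) = 372, or 373 with the planned interim look.
- Power at 384 = Φ(√(384 × 0.2222) × 0.3567 − 1.960) = Φ(1.335) = 0.909, or 0.908 with the interim look.

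So 384 is consistent with 90% power, but it says nothing about ECOG events.

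**3. How far apart the two readings are**

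A three-state model (not deteriorated, deteriorated, dead) gives an illustration.

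- From the documents: control median OS 5 months, death HR 0.70 (applied within each state), 2:1 allocation, 18 months' accrual (taken as uniform), 8 months' further follow-up, ECOG every 28 days and at the 30-day visit.
- Assumed, not in the documents: deterioration hazard 0.08, 0.15 or 0.25 per month; deterioration HR 1.0 or 0.7; death hazard 4 times higher after deterioration; median time on treatment 1.7 months on placebo and 1.7 or 2.5 months on TAS-102, independent of outcome; 5%/year loss ignored.

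The control death hazard h before deterioration solves S(5) = 0.5, with λ the deterioration hazard and
S(t) = e^(−(h+λ)t) + [λ/(h+λ−4h)] × [e^(−4ht) − e^(−(h+λ)t)].
For λ = 0.15, h = 0.0821: 0.313 + (−1.558)(0.194 − 0.313) ≈ 0.50.

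Results per 500 patients; ranges cover the two treatment-duration settings:

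| λ | Deterioration HR | Events, death not scored | Events, death = 5 | Deaths censored | HR, death not scored | HR, death = 5 |
|---|---|---|---|---|---|---|
| 0.08 | 1.0 | 81–92 | 437–438 | 347–357 | 0.99–1.05 | 0.82–0.83 |
| 0.08 | 0.7 | 66–74 | 425–426 | 352–360 | 0.70–0.74 | 0.74–0.75 |
| 0.15 | 1.0 | 141–157 | 452–455 | 298–312 | 0.98–1.04 | 0.86–0.87 |
| 0.15 | 0.7 | 119–132 | 438–441 | 309–320 | 0.69–0.73 | 0.74 |
| 0.25 | 1.0 | 210–229 | 464–467 | 238–254 | 0.98–1.02 | 0.89–0.92 |
| 0.25 | 0.7 | 180–198 | 452–454 | 256–271 | 0.70–0.72 | 0.73–0.76 |

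Within a setting the two event counts differ by the censored deaths, up to rounding (229 + 238 = 467). By arm, about 50% to 86% of deaths have no earlier recorded 2 or higher.

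**4. Limits of the illustration**

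The model stops at a fixed time, not at 384 deaths, and it runs past that number. Where 360 deaths are censored, the arm-level shares are 0.841 and 0.856, so total deaths lie between 360/0.856 = 421 and 360/0.841 = 428. Applying 50–86% to the plan's 384 deaths gives roughly 192–330 censored deaths. That is smaller, but still large beside the recorded events.

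**The case against.** The strongest objection is that the plan may already count death. Read literally, a patient at score 5 has reached the event and is outside the censoring sentence; the synopses' reference to PFS points the same way; and the text blacked out after the SAP sentence, or the blacked-out data-handling rules, may say so outright. This stands. A reader might infer that the plan censors deaths informatively as a matter of fact. The documents do not support that: they show an unsettled rule, and they do not show how the case report form or the derivation codes score 5. What remains is that the definition sections and the Protocol's analysis section state no death rule, so the visible texts need aligning in any case.

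Second, censoring deaths distorted little in the model: the HR was 0.98–1.05 when treatment had no effect on deterioration, and 0.69–0.74 when the true value was 0.7. This also stands, within limits. The model made treatment stopping independent of outcome, whereas Protocol 8.5.1 lists progression and intolerable toxicity among the reasons for stopping, so the main route by which censoring could depend on prognosis was not tested.

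Third, counting death makes the endpoint a composite. With no effect on deterioration it gave an HR of 0.82–0.92, an apparent benefit that comes from survival alone. This is a good reason not to insist on death as an event in the main analysis.

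**Conclusion.** The point holds as an unresolved inconsistency. The visible plan does not say consistently whether death is an event, a competing event or a censoring reason for this endpoint, nor on what date. Unless death is scored as 5, deaths without an earlier recorded 2 or higher are censored at the last ECOG visit, and that censoring is informative.

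The illustration puts the two readings at roughly 66–229 and 425–467 events per 500 patients, with about 240–360 deaths moving between event and censored. These figures rest on assumed deterioration rates and treatment durations and show order of magnitude only. No direction of bias can be claimed: counting death lowered the HR when treatment did not affect deterioration, and raised it slightly when the deterioration HR was 0.7.

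A reader might also infer that nearly all censored patients have died. The planned cut-off of 384 deaths among 500 patients leaves 116 alive, so that does not follow.

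This is an other-secondary endpoint. The OS test, its 384 deaths and the PFS test are unaffected. What changes is what can be concluded from the ECOG comparison at the 2-sided 0.05 level.

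**What to change.** - State once, before unblinding, whether death is an event, a competing event or a censoring reason for this endpoint, and which date applies.
- Align the two synopses, the definitions (Protocol 13.2.3.3, SAP 3.2.3.3) and the analysis sections (Protocol 13.3.2.3, SAP 10.4.4.3) with that rule. If the blacked-out text already contains it, bring the other places into line.
- Pre-specify the other reading as a sensitivity analysis: if the main analysis uses observed scores, count death as an event on the date of death.
- Report by arm the number of deaths censored without an earlier recorded score of 2 or higher.

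The cost is a few sentences and one extra table from data already collected. The downside is that the death-as-event version is a composite that partly reflects OS, and it should be labelled as such.

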10.4.4.4. Quality of Life

Analysis of the EORTC QLQ-30 and QLQ-STO22 questionnaire should follow the instructions described in the manual created by the developers of the questionnaire. The manual SCManualQLQ-C30 can be found on the EORTC site <http://www.eortc.be/qol/files>. Note that the document contains SAS programs for correct calculation of scoring.

The QLQ-30 is composed of both multi-item scales and single-item measures. These include five functional scales, three symptom scales, a global health status / QoL scale, and six single items. Each of the multi-item scales includes a different set of items - no item occurs in more than one scale. The QLQ-STO22 is composed of 5 multi-item scales and 4 single-item measures.

Assignment of the QoL test to the appropriate cycle will be performed according to the instructions displayed in CCI. Additionally, if multiple QoL tests are reported at an analysis time window (refer to [Section 8.7](#) CCI), then the logic described in [Section 8.8](#) and specific data handling rules presented in CCI will be applied.

10.4.4.4.1. Compliance

Questionnaire compliance rates (for all measures - both multi-item scales and single-item ones), will be assessed at each measurement time point (baseline, prior to cycle 2, 3, 4, etc.) and presented as a separate table.

10.4.4.4.2. Missing Values

If at least half of the items in multi-item scale is not missing, the standard instructions described in aforementioned manual will be applied for calculation of the scale scores and any item with missing value will be ignored when the calculations is performed. If less than half of the items in multi-item scale is not missing than the scale score will be set to missing. If the item is missing in the single-item measure, than the score of this measure will be set to missing.

10.4.4.4.3. Internal Consistency and Reliability

Internal reliability and consistency of the multi-item scales (five in QLQ-30 and five in QLQ-STO22) will be assessed using Cronbach's alpha approaches and the results will be presented in the separate table.

10.4.4.4.4. Analysis – Descriptive Statistics

Descriptive statistics (for all measures - both multi-item scales and single-item ones) for the summary scores, will be provided for each assessed time point. The statistics will include number of subjects, number of non-missing/missing scales, mean, standard deviation, median, minimum

and maximum. The results will be summarized for the actual and change from baseline values for all available scales and study visit time points.

10.4.4.4.5. Deterioration vs Stable Proportion

For each EORTC QLQ-C30 and QLQ-STO22 score, deterioration in QoL will be defined as a decrease in the score from baseline level of at least five points, the threshold proposed by Osoba et al. [21] as a small but meaningful change in QoL. For each EORTC QLQ-30 and QLQ-STO22 measure, the proportion of patients with deteriorating and (stable or improving) scores at weeks 4, 8 and 12 will be compared using Fisher's exact test. The results will be summarized as a separate table.

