13.3.2.3. Secondary Endpoint Analyses

All secondary endpoints comparisons will be made at the 2-sided 0.05 significance level. Since PFS is the only key secondary endpoint for regulatory registration purposes, no further multiplicity adjustments will be made. Assuming that OS demonstrates significance at the 1-sided 0.025 level, PFS can subsequently be tested at the 2-sided 0.05 level.

PFS

PFS will be analyzed with the methodology specified in Section 13.3.2.1 and Section 13.3.2.2a, c, and d. CCI

ORR and DCR

The treatment comparison for ORR and DCR will be based on the TR population using Fisher's exact test. Treatment estimates and differences will be presented along with the associated 95% CIs.

Time to Deterioration of ECOG Performance Status

Time to deterioration of ECOG performance status to a score of 2 or higher will be analyzed using methodology described in Section 13.3.2.1. Patients not reaching an ECOG of 2 or more (3, 4 or 5) will be censored at the last recorded ECOG assessment.

Quality of Life

Questionnaire compliance rates, for both scales, will be assessed at each measurement time point (baseline, prior to cycle 2, 3, 4, etc.).

Descriptive statistics, for both scales, for the summary scores, as well as the subscale scores will be provided for each assessed time point. In addition, change in QoL scores at representative time points will be determined for the summary, all domains and single items by subtracting each patient's score from their corresponding baseline score. Representative time points will be prior to cycle 2, 3 and 4, chosen based on expected patient compliance to be adequate to allow meaningful analyses, considering the expected treatment duration in the two study groups.

For each domain, the proportion of patients with deteriorating, stable or improving scores prior to cycles 2, 3 and 4 will be compared using Fisher's exact test. In addition, time to QoL deterioration will be evaluated for each arm using Kaplan-Meier estimates and compared using the log-rank test. The criteria for deteriorating, stable or improving scores will be detailed in the SAP.

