3.2.3.4. Quality of Life

The EORTC quality of life questionnaire (QLQ) is an integrated system for assessing the health related quality of life (QoL) of cancer patients participating in international clinical trials. The core questionnaire, the QLQ-C30, incorporates 5 functional scales (physical, role, cognitive, emotional, and social), 3 symptom scales (fatigue, pain, and nausea and vomiting), a global health status scale, and a number of single items assessing additional symptoms commonly reported by cancer patients

(dyspnea, loss of appetite, insomnia, constipation and diarrhea) and perceived financial impact of the disease.

The gastric cancer module (QLQ-STO22) is meant for use among gastric cancer patients varying in disease stage and treatment modality.

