8.4. Change from Baseline

Change from baseline is calculated as (post-baseline result – baseline result).

Percent change from baseline is calculated as (change from baseline/baseline result * 100).

If either the baseline or the post-baseline result is missing, the change from baseline and/or percentage change from baseline is set to missing as well.

8.5. Day 1

The date of first administration of study medication (first dosing) is defined as Day 1 of treatment (D1). The date of first administration of study medication (first dosing) within the Cycle N is defined as Day 1 of the Cycle N (CND1).

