10.4.4.4.6. Time to Deterioration – Main Analysis

Time to first deterioration in QoL (refer to [Section 10.4.4.4.5](#) for definition) will be evaluated for each arm using Kaplan-Meier estimates and compared using the log-rank test (and Cox proportional hazards models adjusting for the baseline value of the EORTC QLQ-C30 and QLQ-STO22 score, country and primary tumour type). Patients with no deterioration in EORTC QLQ-C30 and QLQ-STO22 scores will be censored at the end of study, cut-off date or death date.

CCI

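### The SAP defines QoL deterioration as a 5-point decrease on every score, so symptom relief counts as deterioration

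*SAP*

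**What the plan says.** SAP section 10.4.4.4.5 opens with "For each EORTC QLQ-C30 and QLQ-STO22 score" and continues that "deterioration in QoL will be defined as a decrease in the score from baseline level of at least five points". It gives no exception by type of scale. The next sentence takes the resulting split, deteriorated against stable or improving, into Fisher's exact tests for each measure at weeks 4, 8 and 12.

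Section 10.4.4.4.6 ("Time to first deterioration in QoL (refer to") refers back to the same definition for the Kaplan-Meier estimates, log-rank tests and Cox models.

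The scores covered are of different kinds. For QLQ-C30, SAP section 10.4.4.4 states: "These include five functional scales, three symptom scales, a global health status / QoL scale, and six single items". Section 3.2.3.4 names "3 symptom scales (fatigue, pain, and nausea and vomiting"; its single items cover dyspnea, appetite loss, insomnia, constipation, diarrhea and financial impact. For the gastric module, section 10.4.4.4 says: "The QLQ-STO22 is composed of 5 multi-item scales and 4 single-item measures". Scoring is referred to the questionnaire developers' manual.

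Protocol section 13.3.2.3 leaves the criteria for deteriorating, stable and improving scores to the SAP, so section 10.4.4.4.5 is the governing text.

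**The concern.** A single direction of change can define deterioration only if every score points the same way. Functional and symptom scores do not, unless one set has been reversed first, and no readable section says that this is done. On a symptom score that rises as the symptom gets worse, the rule captures improvement.

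This is not a loss of precision. A patient with worsening nausea is classed with the stable and improving patients, and a patient whose nausea eases becomes an event. A patient who starts at the lowest possible symptom score can never be counted as deteriorated. An arm with more symptoms can therefore appear to preserve QoL better.

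The likely bias has a direction. Protocol section 6.2.3 reports that treatment-related nausea, decreased appetite, diarrhea and vomiting were common on TAS-102 in the earlier colorectal trial (20.1% to 39.4%). Those are domains on which the rule would favor the active arm. QoL is a listed secondary endpoint, tested at the 2-sided 0.05 level, in a SAP meant to support a marketing application.

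**Working it through.** The plan gives no power or event figure for QoL, so there is nothing to reproduce. The check has three parts.

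**1. Scores affected (counts from SAP section 10.4.4.4)**

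- QLQ-C30: 5 functional + 3 symptom + 1 global + 6 single items = 15. A decrease is the right direction for 5 + 1 = 6 and the wrong one for 3 + 6 = 9.
- QLQ-STO22: 5 + 4 = 9. The documents do not give the direction of these scores, so between 0 and 9 are affected.
- Total: 15 + 9 = 24. Affected: from 9 of 24 (38%) to 18 of 24 (75%).

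**2. Who is flagged, one arm**

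Assumptions, not from the documents: a higher symptom score is worse, and the change from baseline is normal with mean +10 (true worsening) and SD between 15 and 30. With Φ the standard normal distribution function:

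- flagged as written: P(change ≤ −5) = Φ((−5 − 10)/SD)
- truly worse by at least 5: P(change ≥ +5) = 1 − Φ((5 − 10)/SD)

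| SD | Flagged as written | Worse by ≥5 |
|---|---|---|
| 15 | Φ(−1.00) = 0.159 | 0.631 |
| 20 | Φ(−0.75) = 0.227 | 0.599 |
| 25 | Φ(−0.60) = 0.274 | 0.579 |
| 30 | Φ(−0.50) = 0.31 | 0.57 |

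**3. Treatment comparison, two arms**

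Assumed mean symptom change: +10 on active, 0 on placebo, same SD in both. With mean 0, the placebo proportion is Φ(−5/SD) under either direction: 0.369, 0.401 and 0.421 for SD 15, 20 and 25. Active minus placebo in the proportion deteriorated (differences taken before rounding):

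| SD | As written | Direction by scale type |
|---|---|---|
| 15 | −0.211 | +0.261 |
| 20 | −0.175 | +0.197 |
| 25 | −0.146 | +0.159 |

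The arm with more symptoms shows 15 to 21 percentage points less deterioration under the rule as written, and 16 to 26 points more when direction follows scale type. The sign reverses at each SD tried. The two columns are not mirror images, because the rule forms a different split of the patients instead of swapping labels.

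**The case against.** Five points can be made for the plan.

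- **Scoring direction is not printed.** The readable text names and counts the scales but does not say that higher means more symptoms. This stands as a stated assumption. It is a mild one: the scales are named for symptoms, and no reversal is described.
- **A correction may exist in text we cannot see.** Section 10.4.4.4 refers the analysis to the developers' manual and to redacted data-handling rules, and text after section 10.4.4.4.6 is redacted. This cannot be excluded. But a different rule there would contradict an explicit definition that covers every score, so the main text would still need correcting.
- **The QLQ-STO22 share is unknown.** This stands, and it is why the extent is given as a range.
- **The descriptive summaries are sound.** Section 10.4.4.4.4 tabulates actual values and changes for all scales, and a careful reader might notice the conflict. That does not repair the tests and survival curves.
- **QoL is an other secondary endpoint.** SAP section 10.3 names PFS as the only key secondary endpoint for registration, so no OS or PFS conclusion depends on this rule. This limits the reach of the error, not the fact that the QoL results would be wrong.

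A related point is separate. Protocol section 13.3.2.3 subtracts each current score from the "score from their corresponding baseline score", and the SAP synopsis repeats this. SAP section 8.4 ("Change from baseline is calculated as") takes post-baseline minus baseline, the opposite sign. The definition of deterioration speaks of a decrease in the score itself, so the sign conflict does not cause the error, but it invites another in programming.

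**Conclusion.** The definition is wrong as written and should be corrected before the QoL data are analyzed. Programmed literally, it misclassifies patients on 9 of 15 QLQ-C30 scores, and on up to 18 of 24 scores if all QLQ-STO22 measures are symptom-type. In the illustrations it flags 16% to 31% of patients where 57% to 63% have worsened by at least 5 points, and it reverses the sign of the arm comparison.

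The conclusion rests on symptom scores rising as symptoms worsen, and on no reversal before analysis. The percentages rest further on the assumed means, SDs and normal changes. The functional scales, global health status, OS and PFS are unaffected.

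**What to change.** In SAP section 10.4.4.4.5, replace the single rule with one by scale type:

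- functional scales and global health status: deterioration is a decrease of at least 5 points from baseline;
- symptom scales, symptom and problem items, and symptom-type QLQ-STO22 scores: deterioration is an increase of at least 5 points.

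List all 24 scores with their direction, taken from the scoring manual. State that section 10.4.4.4.6 uses the same table, and check the redacted handling rules against it. Use post-baseline minus baseline throughout, and align the SAP synopsis and the protocol wording with section 8.4.

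The cost is a sentence or a short table in the SAP and one direction flag per score in the programs. No new data are needed.
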